#### Rate of Relapse (Recurrence)

For each age category, the number of included patients, number of patients who relapsed, and the percent relapsed will be calculated. The denominator for the rate is the number of subjects in that population at baseline. This analysis will be done in the MITT analysis set for the Week 2 and Week 6 FU visits.

This analysis will also be performed for each *Candida* species, combining across the age groups.

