### **Microbiological Response**

**Eradication or presumed eradication:** Baseline pathogen not isolated from original site culture(s), or culture data are not available for a subject with successful clinical outcome.

**Persistence (documented or presumed):** Any baseline *Candida* sp. is present in repeat cultures, or culture data are not available for subject with a clinical outcome of failure.

**Indeterminate:** Culture data are not available for a subject with a clinical outcome of indeterminate.

**Relapse (recurrence):** Any baseline *Candida* sp. isolated following eradication (documented or presumed); or culture data are not available for a subject with a clinical response of failure after a previous response of success; prophylactic treatment with oral antifungal agents is not sufficient to document a relapse.

**New Infection:** Subject presenting with clinical failure with the emergence of new *Candida* sp. at the original site of infection or at a distant site of infection;

A global response determination of failure at the 2 Week Follow Up will be carried forward programmatically to all subsequent visits.

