#### **6.1.5.1. Rate of Relapse at the 2 and 6 Week Follow-Up Visits**

The rate of relapse, defined as a microbiologic response of relapse, at the 2 and 6 Week Follow-Up Visit will be reported.

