### 8.2.2. Secondary Analyses

#### Global Response

For each age category, analysis of global response rate at EOIVT, EOT, 2 weeks FU, and 6 weeks FU will be produced for the MITT analysis set. The summary will include the number of observations and estimated rates overall and for each age category.

This analysis will also be performed for each *Candida* species, combining across the age groups.

In order to investigate the robustness of the results, a sensitivity analysis will be carried out. This analysis will investigate the effect of 'indeterminate' and 'missing' global response on the analysis by excluding these subjects from the analysis of global response.

Analysis of global response success rate only for those subjects who completed study treatment at EOIVT, EOT, 2 week follow-up and 6 week follow-up visits will be produced for the MITT population.

A summary of Global Response, Clinical Response and Microbiological response will be produced for the MITT population. For Clinical Response, this will give a count of the number of subjects in each of the categories 'Cure', 'Improvement', 'Failure', 'Indeterminate', and 'Missing'. For Microbiological response, this will give a count of the number of subjects in each of the categories 'Eradication', 'Presumed Eradication', 'Persistence', 'Indeterminate', and 'Missing'. This will be presented overall, for each age category and for each *Candida* species.

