#### Time To Death

Time to death (all-cause) will be analyzed using methods of [Section 8.1.2](#), on the MITT analysis set.

For each age category, the number of patients who died, who were censored during the study, and who were still alive at each FU visit will be summarized by age stratum.

This analysis will also be performed for each *Candida* species, combining across the age groups.

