**8.2.5. Summary of Efficacy Analyses**

Endpoint	Analysis Set	Statistical Method	Model/ Covariates/ Strata	Missing Data	Interpretation
Rate of global response at EOIVT	MITT	Descriptive only	Age categories	Failure	Secondary Analysis
Rate of global response at EOIVT	MITT	Descriptive only	Age categories	Missing and indeterminate excluded	Sensitivity
Rate of global response at EOIVT	MITT	Descriptive only	Candida species	Failure	Secondary Analysis
Rate of global response at EOIVT	MITT	Descriptive only	Site of infection	Failure	Secondary Analysis
Rate of global response at EOT	MITT	Descriptive only	Age categories	Failure	Secondary Analysis
Rate of global response at EOT	MITT	Descriptive only	Candida species	Failure	Secondary Analysis
Rate of global response at EOT	MITT	Descriptive only	Site of infection	Failure	Secondary Analysis
Rate of global response at Week 2 FU	MITT	Descriptive only	Age categories	Failure	Secondary Analysis
Rate of global response at Week 2 FU	MITT	Descriptive only	Candida species	Failure	Secondary Analysis
Rate of global response at Week 2 FU	MITT	Descriptive only	Site of infection	Failure	Secondary Analysis
Rate of global response at Week 6 FU	MITT	Descriptive only	Age categories	Failure	Secondary Analysis
Rate of global response at Week 6 FU	MITT	Descriptive only	Candida species	Failure	Secondary Analysis
Rate of global response at Week 2 FU	MITT	Descriptive only	Site of infection	Failure	Secondary Analysis
Rate of relapse at Week 2 FU	MITT	Descriptive only	Age categories	Not Applicable	Secondary Analysis
Rate of relapse at Week 2 FU	MITT	Descriptive only	Candida species	Not Applicable	Secondary Analysis

Rate of relapse at Week 6 FU	MITT	Descriptive only	Age categories	Not Applicable	Secondary Analysis
Rate of relapse at Week 6 FU	MITT	Descriptive only	Candida species	Not Applicable	Secondary Analysis
Rate of new infection at Week 2 FU	MITT	Descriptive only	Age categories	Not Applicable	Secondary Analysis
Rate of new infection at Week 2 FU	MITT	Descriptive only	Candida species	Not Applicable	Secondary Analysis
Rate of new infection at Week 6 FU	MITT	Descriptive only	Age categories	Not Applicable	Secondary Analysis
Rate of new infection at Week 6 FU	MITT	Descriptive only	Candida species	Not Applicable	Secondary Analysis
All-cause mortality rate at EOIVT	MITT	Descriptive only	Age categories	Death	Secondary Analysis

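### Relapse is reported only as a share of all MITT subjects at baseline; adding a rate among children at risk of relapse would make it easier to interpret, at little cost

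*SAP*

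**What the plan says.** SAP 8.2.2, Rate of Relapse, plans the number and percentage relapsed at the Week 2 and Week 6 follow-up visits in the MITT set, by age category and by *Candida* species. It fixes the divisor: "The denominator for the rate is the number of subjects in that population at baseline". MITT entry (SAP 5.1) requires one dose and a confirmed infection, with no condition on response.

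The relapse definition in SAP 6.1.3 has two limbs, and both need a prior good state. Under the first, a baseline *Candida* is "isolated following eradication (documented or presumed"). Under the second, cultures are unavailable in a child with "a clinical response of failure after a previous response of success".

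On timing, SAP 6.1.5.1 reads: "The rate of relapse, defined as a microbiologic response of relapse, at the 2 and 6 Week Follow-Up Visit will be reported". The carry-forward rule in SAP 6.1.3 concerns a different variable: "A global response determination of failure at the 2 Week Follow Up will be carried forward programmatically to all subsequent visits".

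In the SAP 8.2.5 table, the missing-data entry for rows such as "Rate of relapse at Week 2 FU" is Not Applicable. In the same table, missing global response counts as failure (apart from the sensitivity row) and missing mortality status counts as death.

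**The concern.** A child with persistent infection throughout treatment cannot relapse under the SAP's own definition, but stays in the denominator as a non-event. So does a child with no follow-up assessment. The SAP does not say this outright; it follows from a fixed baseline denominator with no missing-data rule. The definition already covers missing cultures after success and then clinical failure, so what remains is children not assessed at all.

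Relapse at Weeks 2 and 6 is a named secondary objective, to be shown by age category. A stratum with poorer response, or with more children lost, can show a lower relapse rate simply because fewer children could relapse or be seen to relapse. A reader who wants to know how often infection returns once cleared will not find that figure among the planned outputs. At stake is interpretation of a descriptive endpoint; no test or decision rule is affected.

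**Working it through.** **Is an at-risk rate planned anywhere?** Protocol 9.2 and SAP 2.2 (secondary objective 5) give no denominator for relapse. SAP 8.2.2 gives the baseline one. Per-protocol analyses are run only where stated (SAP 8.2), and none is stated for relapse. The sensitivity analysis that drops indeterminate and missing children works by "excluding these subjects from the analysis of global response", and the treatment-completer analysis is also for global response only. The microbiological summary counts eradication, presumed eradication, persistence, indeterminate and missing, but its category list omits relapse and new infection. No at-risk rate is planned.

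**Relation between the two rates.** Let N be the MITT subjects at baseline, A those at risk and R the relapses, all arising within A. Then

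R/N = (R/A) × (A/N).

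The planned rate is the at-risk rate multiplied by the share at risk, so it cannot exceed that share.

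**Inputs.** N is about 60 (SAP 2.1.2), with about 20 per age stratum (SAP 3.1). The plan states no relapse rate to reproduce. R and A are assumptions. The only response figure in the documents is adult: 75.6% global success at EOIVT (Protocol 1.3.2), and 0.756 × 60 = 45.4, or about 45. I show shares at risk of 60%, 75% and 90%. Intervals are exact 95% Clopper-Pearson, the method SAP 8.1.1 names for response and mortality rates.

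| Five relapses | Rate | 95% CI |
|---|---|---|
| Planned, 5/60 | 8.3% | 2.8 to 18.4 |
| 90% at risk, 5/54 | 9.3% | 3.1 to 20.3 |
| 75% at risk, 5/45 | 11.1% | 3.7 to 24.1 |
| 60% at risk, 5/36 | 13.9% | 4.7 to 29.5 |

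The shift is 9.26 − 8.33 = 0.9 points at 90% at risk and 11.11 − 8.33 = 2.8 points at 75%. Every at-risk estimate in the table lies inside the planned interval.

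**Age strata.** Take two strata of 20 with 2 relapses each. Both show 2/20 = 10.0% (1.2 to 31.7) as planned. With 18 and 15 at risk they show 2/18 = 11.1% (1.4 to 34.7) and 2/15 = 13.3% (1.7 to 40.5).

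**Unassessed children.** With 45 at risk and 3 or 6 never assessed at follow-up, the rate over those assessed is 5/42 = 11.9% (4.0 to 25.6) or 5/39 = 12.8% (4.3 to 27.4), against 11.1% over all 45.

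**Week 6 counting.** Suppose 3 children relapse at Week 2 and 2 more are first seen to relapse at Week 6. A cumulative count gives 5/60 = 8.3%. A visit-specific count lies anywhere from 2/60 = 3.3% (0.4 to 11.5) to 5/60, because a Week 2 relapser whose baseline *Candida* is still isolated at Week 6 meets the definition again.

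**The case against.** The strongest reply is that nothing here is broken. The denominator is written down and the study is descriptive with no hypothesis testing (SAP 4.1). A baseline MITT denominator also avoids conditioning on a post-baseline outcome, which an at-risk rate cannot avoid. That stands, and it is why the planned figure should be kept. A reader might infer that the SAP's relapse rate is wrong or invalid; the documents do not support that.

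Much related information is already planned. Response categories, including missing, are tabulated by age, and SAP 8.2.2 also says the number of patients "who were still alive at each FU visit will be summarized by age stratum". This is largely right, but none of it is given within the group at risk, and that group itself is not tabulated.

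A reader might also infer that the Week 6 rate is open to two programming readings, 3.3% or 8.3%. That goes too far. SAP 6.1.5.1 and 8.2.2 both tie relapse to the visit, whereas SAP 6.1.5.3 words mortality cumulatively, as deaths by each timepoint. The natural reading of the relapse rate is visit-specific, and the two figures are only the extremes. One clarifying sentence is enough.

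Two cautions on the evidence also stand. The adult 75.6% needs clinical and microbiological success together at EOIVT, whereas eradication alone puts a child at risk, so it may understate the share at risk. And the table list in SAP Appendix 2 covers an interim analysis of the two older cohorts, so absence from it says little about the final tables.

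**Conclusion.** The point holds as a cheap improvement, not as the correction of an error. The planned relapse rate is a valid crude proportion of treated, confirmed cases. On its own it does not show how often infection returns among children who could relapse, and its comparison across age strata also reflects response and completeness of follow-up.

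The illustrated shift of 0.9 to 2.8 points for five relapses in 60 rests on assumed relapse counts and an assumed 75% to 90% at risk, and it is within sampling uncertainty. In strata of 20 the intervals are far too wide to separate 10.0% from 13.3%. The gain is a clearly defined quantity, not a changed conclusion.

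**What to change.** In SAP 8.2.2, keep the MITT-baseline proportion and name its denominator in the table label. Add, overall and by age stratum, the cumulative proportion relapsed by Week 2 and by Week 6 among MITT subjects whose status at EOT, their last on-treatment assessment, was documented or presumed eradication or success. Use this one fixed denominator at both visits, so that the two figures are comparable and a child with persistence at EOT is not counted as at risk because of an earlier EOIVT result. Show deaths without recorded relapse and unassessed children as separate categories. List separately any relapse in a child who first reached eradication or success after EOT, so that it is not lost.

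In SAP 6.1.5.1, state that the existing rate is visit-specific and the added rate cumulative. In the SAP 8.2.5 table, replace the Not Applicable entry for relapse with a rule that unassessed children are shown separately and not silently counted as non-events.

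The cost is some SAP wording, one derived flag and one table block from data already collected. The price is a smaller denominator, a wider interval and a group selected after baseline, which a footnote should say.

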#### Rate of New Infection

For each age category, the number of included patients, number of patients with new infection, and the percent with new infection will be calculated. The denominator for the rate is the number of subjects in that group and analysis set at baseline. This analysis will be done in the MITT analysis set for the Week 2 and Week 6 FU visits.

This analysis will also be performed for each *Candida* species, combining across the age groups.

#### All-cause Mortality

For each age category, all cause mortality during study therapy and FU visits will be performed in the MITT analysis set using the same methods described in [Section 8.1.1](#)

All causes of death will be summarized.

This analysis will also be performed for each *Candida* species, combining across the age groups.

#### Time To Death

Time to death (all-cause) will be analyzed using methods of [Section 8.1.2](#), on the MITT analysis set.

For each age category, the number of patients who died, who were censored during the study, and who were still alive at each FU visit will be summarized by age stratum.

This analysis will also be performed for each *Candida* species, combining across the age groups.

### **8.2.3. Analyses for PK-PD Data**

The analyses in support of the PK-PD objective will be described in a separate document.

### **8.2.4. Safety Analyses**

No formal statistical analyses are planned for safety data. The safety and other endpoints detailed in [Section 6.2](#) will be listed and summarized in accordance with sponsor reporting standards, where the resulting data presentations will consist of subjects from the safety analysis set. Additionally, demography, medical history and adverse events will be presented separately for the MITT population.

**8.2.4.1. Treatment and Disposition of Subjects**

Subject disposition and the number of subjects analyzed for efficacy, and safety (adverse events and laboratory data) will be presented by age category. Frequency counts will be supplied for subject discontinuation(s) by age category.

Data will be reported in accordance with the sponsor reporting standards.

**8.2.4.2. Demographic Data and Medical History**

Frequencies for demographic data will be provided for age, race, height, and weight. Each will be summarized by sex at birth and 'All Subjects' for each age category separately and overall in accordance with the sponsor reporting standards.

The subjects in the PK population analysis set will have an additional table summarizing their demography.

Medical history will be summarized overall and by each age category.

**8.2.4.3. Primary Diagnosis and Site of Infection**

Primary diagnosis will be summarized for each treatment group, and will also be cross tabulated with the site of infection. The sites of infection will be collapsed into 3 categories for summarization purposes:

- i. Blood only;
- ii. Blood and other sterile site;
- iii. Sterile site (other than blood) only.

**8.2.4.4. Discontinuation(s)**

Frequency of subject discontinuations, temporary discontinuations or dose reductions due to adverse events will be detailed and summarized by age category.

Data will be reported in accordance with the sponsor reporting standards.

**8.2.4.5. Adverse Events**

All adverse events will be coded using the MedDRA dictionary. Frequencies of adverse events will be presented by system organ class, preferred term, age category, and severity level.

All causality treatment emergent adverse events will be presented using two different treatment groupings.

Firstly they will be presented for the one group where all adverse events are counted from start of study to end of follow-up period. This will provide an overall assessment of all adverse events in the study.

Secondly they will be split into time periods within the study:

- Those that occurred from start of study to end of treatment by anidulafungin, including up to end of follow-up period if no other antifungal was administered;
- Those adverse events that started after treatment with another antifungal up until the end of the follow-up period.

This will provide guidance as to which adverse events occurred during treatment with anidulafungin, as opposed to those that occurred during other therapies.

Treatment related treatment emergent adverse events will be presented in two ways:

- Firstly, for those that are considered to be caused by anidulafungin, providing a summary of treatment related adverse events;
- Secondly, for those that are caused by anidulafungin and/or fluconazole, providing a summary of adverse events for the anidulafungin plus fluconazole treatment regimen.

All causality treatment emergent adverse events and treatment related adverse events will also be summarized for the 6 subjects in the PK sub-study analysis set.

Adverse events and serious adverse events will be listed by subject for all age categories.

Adverse events leading to discontinuation or temporary dose reduction will be presented ([Discontinuation\(s\)](#) Section).

Adverse events will be reported in accordance with the sponsor reporting standards.

Additional tables summarizing adverse events that are considered to be potentially indicative of an infusion related reaction which occur during the anidulafungin infusion or within 60 minutes following completion of the anidulafungin infusion will be presented. The adverse event terms of interest are:

Rash, pruritus, chest tightness, vasodilation, flushing, hyperhydrosis, angioneurotic edema, erythema, urticaria, shortness of breath, cough, feeling hot, sweating, diaphoresis, facial swelling plus possible other similar terms to be determined at the end of study. There will be one table for all causality and another for anidulafungin treatment related.

For subjects with infusion reactions or potential infusion related adverse events who also received anesthetic at the same time, the adverse event will be listed along with the anesthetic administered with the relevant start and stop times.

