- Eradication or presumed eradication of *Candida* sp. from any other sites of infection identified at enrollment;
- The specific *Candida* isolate identified at study entry is susceptible (or presumed to be susceptible based on the species identified and local *Candida* sp. resistance patterns) to fluconazole;
- Signs and symptoms of *Candida* infection have improved such that the Investigator feels it is appropriate to switch to oral fluconazole.

Subjects will receive treatment (either solely IV anidulafungin, or anidulafungin followed by oral fluconazole) for a minimum duration of 14 days from the time of the last of negative culture (defined as the second of two consecutive negative cultures, separated by at least 24 hours, following the last positive culture) and improvement of clinical signs and symptoms of candidemia or invasive candidiasis.

Subjects without microbiologically confirmed *Candida* infection will be treated with IV anidulafungin at the discretion of the investigator to a maximum of 35 days. Subjects may be switched to oral fluconazole (6-12 mg/kg/day, maximum 800 mg/day) after at least 5 days of IV anidulafungin treatment.

The maximum total treatment duration for all subjects in this study is 49 days, and the maximum allowed treatment duration with anidulafungin is 35 days. The last day of study treatment will be considered the End of Treatment (EOT). It is expected that the majority of subjects will receive study drug in the hospital; subjects will be permitted to complete study medication on an outpatient basis if deemed appropriate by the investigator.

*(This paragraph, as it relates to subjects with Candida endocarditis and Candida osteomyelitis is not applicable to Korean and Portuguese investigator sites.)* In subjects with *Candida* endocarditis and *Candida* osteomyelitis who require continued treatment beyond the maximum total treatment duration (49 days), this treatment will be considered outside the context of this clinical trial and study drug will not be supplied by the Sponsor. For the purpose of study treatment evaluation, Day 35 (for subjects who require continued IV treatment) or Day 49 (for subjects who required continued oral therapy) will be considered the last day of study drug treatment. These subjects are also required to return for the 2-week and 6-week follow-up visit following the last dose of study drug.

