In the event the investigator chooses to administer anidulafungin in combination with a second antifungal agent, anidulafungin will be discontinued following the obtainment of required blood samples for pharmacokinetic analysis as specified by the protocol; the data from these subjects will not be utilized for secondary efficacy endpoint analyses but will be assessed for safety. After the dosing regimen is confirmed by the Sponsor, enrollment will be opened to additional subjects within this age group at all investigator sites. Subsequent to this time point, the use of a second systemic antifungal agent (eg, amphotericin B) will not be permitted in any subject.

[figure not shown]
A population PK-PD analysis will also be performed in all other subjects enrolled and will include subjects <2 years of age who are not part of the 6 subject cohort described above, in which 3 to 5 sparse pharmacokinetic samples will be collected. Additionally, at the request of PDCO, pharmacokinetics of polysorbate 80, a solubilizing agent contained in the IV formulation of anidulafungin, will also be explored.

Efficacy will be based on a determination of global response (combination of clinical and microbiological response) of success or failure at the EOIVT, EOT, 2-week FU and 6-week FU visits. Rates of relapse (recurrence) and/or new infection will be assessed at the FU visits. Safety will be evaluated through assessment of adverse events and monitoring of clinical laboratory tests (hematology and serum chemistry), temperature, and physical examination results. All subjects will be followed for safety through the 6-week FU visit.

The planned enrolment is approximately 60 evaluable subjects (those subjects who have received at least one dose and confirmed *Candida* infection).

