##### 4.1. Inclusion Criteria

Subject eligibility should be reviewed and documented by an appropriate qualified member of the investigator's study team before subjects are included in the study.

Subjects must meet all of the following inclusion criteria to be eligible for enrollment into the study:

1. Subject must be either (1) at high risk for candidiasis or (2) have a definitive diagnosis of invasive candidiasis/candidemia (ICC), as defined below:
  - a. **At high risk for candidiasis (subjects 1 month to < 2 years of age only):**  
Subject is at high risk for candidiasis and antifungal therapy with anidulafungin for a minimum of 5 days is considered appropriate by the investigator.

--OR--

- b. **Definitive diagnosis of invasive candidiasis/candidemia (ICC) (all age groups)**  
is based on the growth of *Candida* sp. from a blood and/or tissue culture obtained from a normally sterile site.

For the purpose of study entry, a subject enrolled with definitive diagnosis of ICC must have at least one microbiologic AND at least one clinical criterion listed below.

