### 6.2.2. Days 1 and 2 ONLY for Sub-study Subjects (first 6 subjects aged 1 month to <2 years at selected sites)

Prior to the administration of the first dose of study drug, a plasma sample (0.1 – 0.2 mL) should be obtained and sent to the reference laboratory to test for assay interference. Excess blood collected for safety laboratory testing may be used for this sample, otherwise it should be collected directly from the subject.

**Pharmacokinetic sampling:** Six (6) blood samples (0.3-0.5 ml each to provide 0.1 – 0.2 mL plasma) will be collected for anidulafungin measurement at the following time points:

- **On Day 1:** 2 minutes before the end of infusion;

- **On Day 2:** Just prior to the start of infusion; 2 minutes before the end of infusion, 6 hours after start of infusion, 12 hours after start of infusion, and 24 hours after start of infusion.
- In the event that the sample required 2 minutes before the end of infusion was not taken at the specified time, every effort must be made to acquire a sample within 5 minutes of the end of infusion with proper and specific time documentation.

Note: In case the subjects are not ready for serial pharmacokinetic sampling on this specific day, this can be re-arranged at a later date when they continue to receive 1.5 mg/kg daily maintenance dose of anidulafungin. The flexibility of the sampling time is also allowed as long as the actual time of collection is recorded in the CRF.

Ideally, the pharmacokinetic (PK) sampling would be taken from a different site/line than the one used for study drug infusion. However, at the discretion of the investigator and with appropriate flushing of the line to clear all drug residues, samples may be collected using the same line.

**\*\* Important Note \*\*** For subjects in whom the investigator has chosen to administer anidulafungin in combination with a second antifungal agent, these subjects will be discontinued from treatment following completion of pharmacokinetic sampling but will remain in the study for continued safety assessments and are required to return for the 2-week and 6-week follow-up visits.

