## **6.4. Covariates**

As this is a descriptive study, there are no covariates needed for this study.

As an objective of the study is to examine safety and efficacy within the different age groups, a number of the variables will be presented split into the age categories: 1 month - <2 years, 2 years - <5 years and 5 - <18 years.

Global response rates for each of the different *Candida* species will also be reported.

Site of infection is of interest to see whether there are different response rates dependent on the site of infection. Global response rates will be presented for each of the three categorizations for rate of response:

- i. Blood only;
- ii. Blood and other sterile site;
- iii. Sterile site (other than blood) only.

Dependent on numbers of subjects, global response may also be presented by different underlying diseases.

- neutropenic status (<500 neutrophils vs  $\geq$ 500 neutrophils.)
- allogeneic BMT vs not allogeneic BMT

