## 8. STATISTICAL METHODOLOGY AND STATISTICAL ANALYSES

### 8.1. Statistical METHODS

#### 8.1.1. Analyses for Binary Data

Response rates and mortality rates at each timepoint will be presented with exact 95% confidence intervals for binomial proportion, using the Clopper-Pearson method which employs the F-distribution to obtain percentiles of the binomial distribution (Collett 1991).

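### Adverse events by age are planned only as crude frequencies, although the two protocol-defined short-exposure routes exist only in the infant stratum; exposure-adjusted rates and exact intervals should be added

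*SAP*

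**What the plan says.** Safety is the primary endpoint (Protocol 2.2, SAP 6.2). SAP 6.4 gives the reason for splitting variables by age: "As an objective of the study is to examine safety and efficacy within the different age groups". The measure itself is in SAP 8.2.4.5: "Frequencies of adverse events will be presented by system organ class, preferred term, age category, and severity level".

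Three rules decide which events count:
- SAP 6.2.1 treats an event as treatment emergent up to 30 days after the last dose.
- The first grouping in SAP 8.2.4.5 runs from study start until follow-up closes.
- The second grouping splits at the end of anidulafungin and extends through follow-up only where no other antifungal was given.

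Treatment duration by age is a separate summary (SAP 8.2.4.8). For intervals, SAP 8.1.1 says: "Response rates and mortality rates at each timepoint will be presented with exact 95% confidence intervals for binomial proportion". Nothing equivalent is stated for adverse events.

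Planned exposure differs by entry route:
- **Sub-study infants on a second antifungal.** Protocol 3: "anidulafungin will be discontinued following the obtainment of required blood samples for pharmacokinetic analysis as specified by the protocol". Protocol 6.2.2 puts the last Day 2 samples at "6 hours after start of infusion, 12 hours after start of infusion, and 24 hours after start of infusion", although sampling may be moved later. SAP 5.3.2 pools these infants into the safety population.
- **At-risk infants, below 2 years only.** Protocol 4.1 requires that "antifungal therapy with anidulafungin for a minimum of 5 days is considered appropriate by the investigator".
- **Confirmed infection, any age.** Protocol 5.1 requires at least 14 days after the second of two consecutive negative cultures.
- **Upper limit.** Protocol 3: "The maximum total treatment duration for all subjects in this study is 49 days", of which at most 35 days are anidulafungin.

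**The concern.** A percentage of subjects with at least one event rises with the time over which events can occur. Here that time is tied to age through eligibility, because both protocol-defined short routes belong to the youngest stratum. Two strata with the same daily risk can therefore show different percentages. The duration table would reveal the imbalance, but a reader could not turn it into a corrected event rate.

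The youngest stratum is also the one for which Amendment 9 broadened enrolment in order to obtain safety data sooner. With about 20 subjects per stratum and no intervals on adverse event proportions, a low or zero count among infants can be taken as more reassuring than it is.

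**Working it through.** **The plan's own figure.** Protocol 9.4 gives 60 evaluable subjects and states that no sample size calculation was done. 3 strata × 20 = 60 (54 to 66 with ± 2). The documents give no adverse event rate, so there is none to reproduce.

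**Counting windows.** With D days of study treatment, D runs from about 2 (two sub-study doses) to 49.
- On treatment only: 2 to 49 days, a ratio of 24.5.
- Treatment emergent, D + 30: 32 to 79 days, a ratio of 2.5.
- Through the 6-week visit, D + 42: 44 to 91 days, a ratio of 2.1.

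**Expected crude percentage.** P = 1 − exp(−λW), with W the window in days. These inputs are assumptions, not in the documents: constant λ of 0.01, 0.02 or 0.05 per day, the same for all ages; 20 subjects per stratum; older children treated 20 days; and the infant mixes below.

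At λ = 0.02, older children give 1 − exp(−0.02 × 50) = 63.2% in the 30-day window and 1 − exp(−0.02 × 62) = 71.1% through follow-up. For infants in the 30-day window, 2 days of treatment gives 47.3% (W = 32) and 5 days gives 50.3% (W = 35). The second mix is then (6 × 47.3 + 7 × 50.3 + 7 × 63.2)/20 = 53.9%.

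| 20 infants, by treatment days | D + 30: infants vs older | D + 42: infants vs older |
|---|---|---|
| 6 at 2, 14 at 20 | 58.4% vs 63.2% | 67.3% vs 71.1% |
| 6 at 2, 7 at 5, 7 at 20 | 53.9% vs 63.2% | 63.8% vs 71.1% |
| 6 at 2, 14 at 5 (extreme) | 49.4% vs 63.2% | 60.2% vs 71.1% |
| 20 at 20 | 63.2% vs 63.2% | 71.1% vs 71.1% |

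Over all three hazards and the three short-exposure mixes, the smallest gap is 2.0 points (first mix, λ = 0.05, D + 42). The largest is 13.8 points (third mix, λ = 0.02, D + 30). With equal durations it is 0.

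**Second grouping, λ = 0.02.** An at-risk infant given 5 days of anidulafungin and no other antifungal is counted for 5 + 42 = 47 days: 1 − exp(−0.94) = 60.9%. An older child switched to fluconazole after 10 days is counted under anidulafungin for 10 days, reading fluconazole as another antifungal: 1 − exp(−0.2) = 18.1%. Here the infant looks worse.

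**Does a rate remove the artefact?** Expected first events divided by expected time to first event or end of window equals λ. At λ = 0.02 every mix gives 2.0 per 100 subject-days in all three windows. This follows by construction from a constant hazard.

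**Intervals.** For zero events the exact upper 95% limit is 1 − 0.025^(1/n): 16.8% for 0/20 and 6.0% for 0/60.

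**The case against.** Several counter-arguments have force.

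**Size.** A reader might compare 2 with 49 treatment days and infer a very large distortion; at λ = 0.02, counting treatment days alone gives 3.9% against 62.5%. The documents do not support that for the main tables, because SAP 6.2.1 and 8.2.4.5 count events well past the last dose. The spread falls from 24.5-fold to about 2.1- to 2.5-fold. The 49 days also include oral fluconazole.

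**Direction.** A reader might infer that every short exposure is an infant's and that infants will look safer. Neither follows. Subjects of any age enrolled on suggestive mycology may stop at the investigator's discretion (Protocol 3, 6.8), and unconfirmed subjects may switch after 5 days with no stated age limit. Five days is an intended minimum, and at-risk infants share the same maxima. The enrolment mix is unknown, and the second grouping can push the other way.

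**Status.** There is no formal safety comparison between ages. SAP 4.1 and 8.2.4 make the analysis descriptive. That stands, but intervals are not tests, and the SAP already gives them for response and mortality.

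**Existing safeguards.** The six sub-study infants get their own adverse event summary and patient profiles (SAP 5.3.2, 8.2.4.5), adverse events are also presented for MITT (SAP 8.2.4), and duration is shown by age. These help, but the sub-study table mixes monotherapy with combination infants, MITT leaves unconfirmed at-risk infants out without showing them on their own, and none of them yields a rate. The sponsor reporting standards are not in the documents, so a rate there cannot be ruled out. The SAP's only table list, Appendix 2, covers the interim analysis of the two older cohorts and names none.

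**Remedy.** Rates per subject-day would suit infusion-related events badly. SAP 8.2.4.5 ties these to the infusion and the 60 minutes after it. If reactions cluster at early infusions (an assumption), dividing by days would flatter the longer-treated children. This objection is accepted in the fix.

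**Conclusion.** The point holds as a limited and cheaply remedied gap. Time at risk differs by age stratum by design, and no adverse event summary named in the SAP accounts for it. In the counting windows actually planned, the crude infant percentage can be about 2 to 14 points lower at identical daily risk. That range rests on the assumed constant hazards, 20 treatment days in older children and the assumed infant mixes; with equal durations the difference is 0. In the second grouping the distortion can run the other way, so the crude percentages can mislead in either direction. The missing intervals are a smaller, separate omission: no events in 20 infants is compatible with a true proportion of up to 16.8%. None of this undermines the trial's descriptive purpose; it limits how the age-specific safety tables can be read.

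**What to change.** In SAP 8.2.4.5, keep the crude frequencies and add:

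1. By age category, for any treatment-emergent event, serious event, treatment-related event and discontinuation due to an adverse event: first events per 100 subject-days at risk, in each planned counting window, with the window stated in the table title.
2. For infusion-related events: occurrence per infusion, or at the first infusion versus later ones, and not per subject-day.
3. Exact 95% confidence intervals on the crude proportions, using the Clopper-Pearson method already in SAP 8.1.1.
4. Within 1 month to <2 years: separate columns for confirmed and unconfirmed infants.

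Reconcile Protocol 3, which requires the 2-week visit of everyone treated, with Protocol 6.5, which requires it only for confirmed infection; otherwise opportunities to record events also differ by confirmation status.

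The cost is a few extra summary columns from dates and culture results already collected. The rates assume a roughly constant hazard, which is why the crude frequencies should stay beside them.
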